4.3. Lifestyle Requirements (Part 1 and Part 2)

The investigator or his or her designee, in consultation with the participant, will confirm that the participant has selected an appropriate method of contraception for the individual participant [and his or her partner(s)] from the permitted list of contraception methods (see list below) and will confirm that the participant has been instructed in its consistent and correct use. At time points indicated in the [Schedule of Activities](#), the investigator or designee will inform the participant of the need to use 2 highly effective methods of contraception consistently and correctly and document the conversation, and the participant's affirmation, in the participant's chart. In addition, the investigator or designee will instruct the participant to call immediately if 1 or both of the selected contraception methods is discontinued or if pregnancy is known or suspected in the participant or partner.

In addition, the investigator or designee will instruct the participant to call immediately if the selected contraception method is discontinued or if pregnancy is known or suspected in the participant or partner.

Highly effective methods of contraception are those that, alone or in combination, result in a failure rate of less than 1% per year when used consistently and correctly (ie, perfect use) and include:

1. Correctly placed copper-containing intrauterine device (IUD).
2. Male condom or female condom used WITH a spermicide (ie, foam, gel, film, cream, or suppository). For countries where spermicide is not available or condom plus spermicide is not accepted as highly effective contraception, this option is not appropriate.
3. Male sterilization with absence of sperm in the postvasectomy ejaculate.

4. Bilateral tubal ligation/ bilateral salpingectomy or bilateral tubal occlusive procedure (provided that occlusion has been confirmed in accordance with the device's label).
 - a. All sexually active male participants must agree to prevent potential transfer to and exposure of partner(s) to drug through ejaculate by using a condom consistently and correctly, beginning with the first dose of investigational product and continuing for; at least 5 months after the last dose of [investigational product OR comedication].

4.4. Sponsor's Qualified Medical Personnel

The contact information for the sponsor's appropriately qualified medical personnel for the study is documented in the study contact list located in the supporting Study Manual and in the team SharePoint Site.

To facilitate access to appropriately qualified medical personnel on study-related medical questions or problems, participants are provided with an Emergency Contact Card (ECC). The ECC contains, at a minimum, (a) Protocol and investigational product identifiers; (b) Participant study numbers; (c) At least 2 emergency phone numbers, active 24 hours/day, 7 days/week, all holidays and weekends, providing a method to contact both the Principal Investigator and the Research Site; and (d) a Pfizer Call Center number.

The ECC is to be used only by outside medical personnel, not involved in the research study, primarily as a means of contacting the Principal Investigator or Research Site related to the care of a study participant. The Pfizer Call Center information is to be used only in the event that, after calling the phone numbers of both the Principal Investigator and Research Site Staff, neither could not be reached in case of an Emergency.

The ECC should be used only in the event that the established communication pathways between the Principal Investigator, the Research site, and the Study Team are not available. Importantly, the ECC is intended to augment, and not to replace, the established communication pathways between the Principal Investigator, the Research site, and the Study Team for advice on medical issues arising during the study. The ECC is not intended for use by the participant directly; if a participant calls the Pfizer Call Center directly, the participant will be directed back to the Principal Investigator or Research site.

5. STUDY TREATMENTS

For the purposes of this study, and per International Conference on Harmonisation (ICH) guidelines, investigational product is defined as a pharmaceutical form of an active ingredient or placebo being tested or used as a reference/comparator in a clinical trial, including a product with a marketing authorization when used or assembled (formulated or packaged) in a way different from the approved form, or when used for an unapproved indication, or when used to gain further information about an approved use (ICH E6 1.33).

For this study, the investigational product VBIR-2 (PF-06936308) consists of:

Reagent	PF #
AdC68, an adenovirus prime vaccination	PF-06871923
pDNA, aPlasmid DNA boost vaccination	PF-06871925
Tremelimumab, an CTLA4 monoclonal antibody	PF-06753388
Sasanlimab, an anti-PD-1 monoclonal antibody	PF-06801591

5.1. Allocation to Treatment

Eligible participants will be enrolled to receive components of VBIR-2 in an open-labeled, unblinded manner. In Part 1, participants will be successively assigned to the next available treatment slot at a dose level decided on after the previous cohort's safety evaluation and ongoing observations of earlier enrolled participants.

Dose level allocation will be performed by the sponsor after participants have given their written informed consent and have completed the necessary baseline assessments. The site staff will email a completed Registration Form to the designated sponsor study team member. The sponsor will assign a participant identification number documenting participant enrollment.

No participant shall receive investigational product until the investigator or designee has received the following information in writing from the sponsor:

- Confirmation of the participant's enrollment;
- Specification of the dose level for that participant;
- Permission to proceed with dosing the participant.

The sponsor or designee will notify the other sites of the inclusion of a new participant, and will inform study sites about the next possible enrollment date.

5.2. Participant Compliance

All doses of adenovirus, pDNA, tremelimumab and sasanlimab will be administered by the appropriately designated study staff at the investigational site. The site will complete the required dosage Preparation Record located in the Investigational Product manual. The use of the Preparation Record is preferred but it does not preclude the use of an existing appropriate clinical site documentation system. The existing clinical site's documentation system should capture all pertinent/required information on the preparation and administration of the dose. This may be used in place of the Preparation Record after approval from the Pfizer monitor.

Participants who fail to comply with the study requirements may be withdrawn from the study.

5.3. Investigational Product Supplies

All components of VBIR-2 will be supplied by Pfizer. VBIR-2 consists of the following components: Adenovirus (AdC68), plasmid DNA (pDNA), tremelimumab and sasanlimab. Sites will be provided with the following supplies:

- PF-06871923 AdC68 Solution for Injection 3×10^{11} VP/mL;
- PF-06871925 pDNA Solution for Injection 2.5 mg/mL;
- PF-06753388 Tremelimumab Solution for Injection 100 mg/mL;
- TDS-IM V 2.0 electroporation device and associated supplies (eg, cartridges) for pDNA administration;
- PF-06801591 Sasanlimab Solution for Injection 50 mg/mL.

Study centers will receive a supply of clinical trial materials upon site activation with instructions on how to confirm drug receipt. Resupplies will be made during the course of the study based on need. Study centers will supply commonly available sterile syringes and needs for IM and SC administration. The details on drug supply will be provided in the Investigational Product Manual (IP Manual). The study monitor should be contacted for any issues related to drug supplies.

5.3.1. Dosage Form(s) and Packaging

PF-06871923 AdC68 Solution for Injection is presented as a sterile solution for intramuscular administration. Each vial contains AdC68 at 3×10^{11} VP/mL in an aqueous buffered solution. Each vial is filled with an adequate volume to eject a minimum 1.0 mL from a syringe with an IM needle attached. The vial is sealed with a stopper and an overseal and labeled according to local regulatory requirements. Two vials will be dispensed per participant, regardless of dose, to facilitate bilateral injection.

PF-06871925 pDNA Solution for Injection, 2.5 mg/mL, is presented as a sterile solution for intramuscular administration. Each glass prefilled syringe (PFS) contains pDNA at 2.5 mg/mL in aqueous buffered solution. The PFS is filled with an adequate volume to eject 1.0 mL when administered using the TDS-IM V 2.0 electroporation device. The PFS is sealed with a plunger stopper and a tip cap and labeled according to local regulatory requirements. Two (2) prefilled syringes will be dispensed per participant.

Each TDS-IM V 2.0 6mm Application cartridge, for unique use, for intramuscular administration of the pDNA solution will be supplied in a sterile tray (one cartridge/tray) labeled according to local regulatory requirements.

PF-06753388 Tremelimumab Solution for Injection is presented as a sterile solution. Each vial contains tremelimumab at 100 mg/mL in aqueous buffered solution. The vial is filled with an adequate volume to eject a minimum 0.75 mL from a syringe with a SC needle

attached. The vial is sealed with a stopper and an overseal and labeled according to local regulatory requirements. Two vials will be dispensed per participant, regardless of dose, to facilitate bilateral injection.

PF-06801591 Sasanlimab Solution for Injection 50 mg/mL is presented as a sterile solution. Each vial contains 100 mg of sasanlimab in 2 mL of aqueous buffered solution, and contains a sufficient amount to ensure an extractable volume of 2 mL. Each vial is sealed with a stopper and an overseal, and labeled according to local regulatory requirements.

5.3.2. Preparation and Dispensing

AdC68, tremelimumab and sasanlimab are provided as single use vials; pDNA is provided as a single use prefilled syringe. They will be packaged and dispensed in cartons with tamper evident seals. The cartons should not be opened until the drug is to be administered. For the adenovirus, pDNA, tremelimumab and sasanlimab, see the Investigational Product (IP) manual and the TDS-IM V 2.0 Instructions for Use for instructions on how to prepare the investigational products for administration.

The TDS-IM v2.0 6mm Application cartridges for the administration of the plasmid are provided for single use, and will be packaged and dispensed in cartons with tamper evident seals. The cartons should not be opened until the time of administration.

Investigational product should be prepared and dispensed by an appropriately qualified and experienced member of the study staff (eg, physician, nurse, physician's assistant, nurse practitioner, pharmacy assistant/technician, or pharmacist) as allowed by local, state, and institutional guidance.

Only qualified personnel who are familiar with procedures that minimize undue exposure to themselves and to the environment should undertake the preparation, handling, and safe disposal of biologic agents.

5.4. Administration

All AdC68 intramuscular injections are given bilaterally. AdC68 will be administered on Day 1 of Cycles 1 and 2. Please refer to the IP manual for full instructions on the dosage and administration.

Plasmid DNA intramuscular injections are given bilaterally. pDNA will be administered beginning on Day 29 of Cycles 1 and 2 and will then be given at 4 week intervals. After Cycle 2, pDNA will continue to be administered every 2 months in the Maintenance Treatment Period. Please refer to the IP manual for full instructions on the dosage and administration of the pDNA and to the TDS-IM V 2.0 Instructions for Use document for the set up and use of the electroporation device. The TDS-IM device should be operated by clinical personnel that have completed the necessary training on device operation.

All IM injections (AdC68 and pDNA) will be given bilaterally in the deltoid muscles or in the vastus lateralis muscles of the quadriceps. Preference should be given to the vastus lateralis muscles when possible.

Tremelimumab will be administered bilaterally subcutaneously at 4 week intervals during Cycles 1 and 2 on the same day as the AdC68 or pDNA dosing as described in the **SCHEDULE OF ACTIVITIES**. After Cycle 2, tremelimumab will continue to be administered every 2 months in the Maintenance Treatment Period. Both AdC68 and pDNA injections should be given prior to tremelimumab administration. Please refer to the IP manual for full instructions on the dosage and administration of tremelimumab.

Tremelimumab is to be administered in close proximity to the vaccination site. If the vaccination is administered in the vastus lateralis, the tremelimumab is to be administered SC in either the lower quadrants of the abdomen or the quadriceps. If the vaccination is administered in the deltoid, the tremelimumab is to be administered SC bilaterally in the outer triceps.

Sasanlimab will be administered bilaterally subcutaneously at 4 week intervals on the same day as the AdC68 or pDNA and tremelimumab during Cycles 1 and 2 as described in the **SCHEDULE OF ACTIVITIES**. The AdC68 or pDNA as well as the tremelimumab doses should be given prior to sasanlimab administration. During the Maintenance Treatment Period, participants will continue to be dosed with sasanlimab at monthly intervals until confirmed disease progression per RECIST. Please refer to the IP manual for full instructions on the dosage and administration of sasanlimab. Sasanlimab is to be administered in close proximity to the vaccination site. If the vaccination is administered in the vastus lateralis, the sasanlimab is to be administered SC bilaterally in the lower quadrants of the abdomen. If the vaccination is administered in the deltoid, the sasanlimab is to be administered SC bilaterally in the outer triceps.

5.4.1. Recommended Dose Modifications

Every effort should be made to administer investigational product on the planned dose and schedule.

In the event of significant toxicity, dosing may be delayed and/or reduced as described below. In the event of multiple toxicities, dose modification should be based on the worst toxicity observed. Participants are to be instructed to notify investigators at the first occurrence of any adverse symptom.

Dose modifications may occur in one of three ways:

- Within a cycle: dosing interruption until adequate recovery and dose reduction, if required, during a given treatment cycle;
- Between cycles: next cycle administration may be delayed due to persisting toxicity when a new cycle is due to start;

- In the next cycle: dose reduction may be required in a subsequent cycle based on toxicity experienced in the previous cycle.

5.4.2. Dosing Interruptions/Delays due to Treatment Related Toxicity

Participants experiencing Grade 3 or 4 potentially treatment related toxicity or intolerable Grade 2 toxicity despite supportive care should have their treatment with all of the components interrupted/delayed. Appropriate follow-up assessments should be done until adequate recovery occurs as assessed by the investigator.

Re-treatment following treatment interruption for treatment related toxicity or at the start of any new cycle may not occur until all of the following parameters have been met:

- ANC \geq 1,000/mm³.
- Platelets count \geq 50,000/mm³.
- Non-hematologic toxicities have returned to baseline or Grade \leq 1 severity (or, at the investigator discretion, Grade \leq 2 if not considered a safety risk for the participant).

If a treatment delay results from worsening of hematologic or biochemical parameters, the frequency of relevant blood tests should be increased as clinically indicated.

5.4.3. If these conditions are met within 2 weeks of treatment interruption or cycle delay, investigational product(s) may be resumed. Refer to section [Dosing Interruptions/Delays due to Non-Related Events](#)

If participants require treatment interruption for reasons other than treatment-related toxicity (eg, surgery) lasting $>$ 4 weeks, treatment resumption should be decided in consultation with the Sponsor.

In the event of active SARS-CoV2 infection confirmed (positive by regulatory authority-approved test) or presumed (test pending/clinical suspicion), the following criteria apply:

- For symptomatic participants with active SARS-CoV2 infection, investigational treatment should be delayed for at least 14 days from start of symptoms.
- This delay is intended to allow resolution of symptoms of SARS-CoV2 infection.
- Prior to restarting treatment, the participants should be afebrile for 72 hours and SARS-CoV2-related symptoms should have recovered to \leq Grade 1 for a minimum of 72 hours.
- Discuss with the Sponsor prior to restarting treatment.
- Consider potential drug-drug interactions (as described per study protocol) for any concomitant medication administered for treatment of SARS-CoV2 infection.

Dose Reductions for adverse events requiring dose reduction at the time of treatment resumption.

If these conditions are not met, treatment resumption must be delayed up to a maximum of 2 weeks. If these parameters have not been met after 2 weeks of dosing interruption or 2 weeks of new cycle delay, permanent discontinuation of treatment should be considered. Treatment resumption for participants recovering from treatment-related toxicity after >2 weeks of treatment interruption or cycle delay may be considered only if the participant is deemed to be deriving obvious clinical benefit per the investigator's best medical judgment and needs to be agreed between the investigator and the sponsor.

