3.4. Toxicities Observed in the Expansion Phase

Adverse events that meet the same grading criteria as the DLT criteria listed above will be discussed promptly by Pfizer and Investigators during the next available Safety meeting. At the meeting, the details of the toxicity will be presented, and actions to be taken (if any) will be discussed, which may involve individual participants, or the Expansion Cohort as a whole.

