5.4.5.1. AdC68 Dose Reductions

Changes in the dose levels for AdC68 will be discussed with the sponsor. Dose reduction of adenovirus by 1 dose level may be allowed in Part 1 depending on the type and severity of toxicity encountered. No dose level reduction is allowed in Part 2. All dose modifications/adjustments must be clearly documented in the participant's source notes and CRF.

Once a dose has been reduced for a given participant, all subsequent cycles should be administered at that dose level for that participant, unless further dose reduction is required. Dose re-escalation for adenovirus is not allowed.

Table 4. AdC68 Available Dose Levels (Part 1)

Dose Level	AdC68*
+1	6×10^{11} VP
Starting	2×10^{11} VP

Table 5. AdC68 Available Dose Levels (Part 2)

Dose Level	AdC68*
Starting	6×10^{11} VP
-1	2×10^{11} VP

Table 6. Dose Modifications for AdC68 Related Toxicity

Toxicity	Grade 1/2	Grade 3	Grade 4
Non-hematologic (other than irAE management described in Appendix 5)	Continue at the same dose level.	Withhold dose until toxicity is Grade ≤ 1 , or has returned to baseline, then resume treatment at the same dose level or reduce the dose by 1 level at the discretion of the investigator*.	Discontinue treatment.
Hematologic	Continue at the same dose level.	Withhold dose until toxicity is Grade ≤ 2 , or has returned to baseline, then resume treatment at the same dose level.	Discontinue treatment.

* Nausea, vomiting, or diarrhea must persist at Grade 3 despite maximal medical therapy to require dose modification.

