5.4.5.2. Tremelimumab Dose Reductions

Changes in the dose levels for tremelimumab will be discussed with the sponsor. A dose reduction of tremelimumab by 1 dose level (from 80 mg to 40 mg) may be allowed depending on the type and severity of toxicity encountered. In addition, an intermediate dose may be considered. Participants requiring a dose level lower than 40 mg will be discontinued from treatment and enter into the follow-up phase unless otherwise agreed between the investigator and sponsor. Algorithms for the management of suspected pulmonary,

gastrointestinal (GI), liver, endocrine, skin, neurological and renal toxicities have been developed (See [Appendix 5](#)). All dose modifications/adjustments must be clearly documented in the participant's source notes and case report form (CRF).

Once a dose has been reduced for a given participant, all subsequent cycles should be administered at that dose level, unless further dose reduction is required. Dose re-escalation for tremelimumab is not allowed.

Table 7. Tremelimumab Available Dose Levels (Part 1)

Dose Level	Tremelimumab
Starting	40 mg
+1	80 mg

Table 8. Tremelimumab Available Dose Levels (Part 2)

Dose Level	Tremelimumab
Starting	80 mg
-1	40 mg

Table 9. Dose Modifications for Tremelimumab Related Toxicity When Given in Combination with AdC68 and pDNA

Toxicity	Grade 1	Grade 3	Grade 4
Non-hematologic	Continue at the same dose level.	Withhold dose until toxicity is Grade ≤ 1 , or has returned to baseline, then resume treatment at the same dose level or reduce the dose by 1 level at the discretion of the investigator.*	Discontinue treatment.
Hematologic	Continue at the same dose level.	Withhold dose until toxicity is Grade ≤ 2 , or has returned to baseline, then resume treatment at the same dose level.	Discontinue treatment.

* Nausea, vomiting, or diarrhea must persist at Grade 3 despite maximal medical therapy to require dose modification.

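### Table 12 and Appendix 5 give opposite instructions for an initial Grade 3 colitis, and the Protocol does not say which dose-modification rule governs

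*Protocol*

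**What the plan says.** Three parts of the Protocol tell an investigator what to do after a treatment-related toxicity.

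- **Section 5.4.2** sets the trigger and the recovery criteria. Participants experiencing "Grade 3 or 4 potentially treatment related toxicity or intolerable Grade 2 toxicity despite supportive care should have their treatment" with all components interrupted or delayed. Re-treatment "may not occur until all of the following parameters have been met": neutrophil and platelet minimums, and non-hematologic toxicity back to baseline or Grade 1 or lower. At the investigator's discretion, the last criterion may instead be at or below Grade "2 if not considered a safety risk for the participant". The text continues: "If these conditions are met within 2 weeks of treatment interruption or cycle delay, investigational product(s) may be resumed". After more than 2 weeks, resumption requires obvious clinical benefit and "needs to be agreed between the investigator and the sponsor".
- **Tables 6, 9 and 12** (section 5.4.5) give the component rules. Table 6 covers AdC68, and its non-hematologic row applies to toxicity "other than irAE management described in Appendix 5". Table 9 is titled "Dose Modifications for Tremelimumab Related Toxicity When Given in Combination with AdC68 and pDNA". Table 12 covers toxicity related to sasanlimab, tremelimumab or both. Its double-asterisk footnote makes discontinuation permanent for Grade 3 or higher colitis or pneumonitis and for any myocarditis. For other conditions it allows a return at Grade 1 or lower or baseline, if investigator and sponsor agree.
- **Appendix 5** gives organ-by-organ management of immune-related events. Sections 5.4.5.2 and 5.4.5.3 point to it without saying whether it overrides the tables.

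For Part 2, section 3.4 adds that events meeting the DLT grading criteria "will be discussed promptly by Pfizer and Investigators during the next available Safety meeting".

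**The concern.** Section 5.4.5.3 sends the investigator to Appendix 5 and then presents Table 12. For an initial Grade 3 colitis the two give opposite answers, so a site that follows one breaches the other. What is at stake is whether a participant is re-dosed with a combined anti-CTLA-4 and anti-PD-1 regimen after an event that another part of the same Protocol treats as a permanent stop. Section 5.4.5.3 itself names colitis, pneumonitis, creatinine and liver test elevation for careful monitoring. Section 1.6.5 reports more toxicity when the two antibody classes are combined. There is no data monitoring committee (section 9.7), so the written rules carry more of the weight.

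**Working it through.** No arithmetic reproduces or refutes a planned figure here; the check is a comparison of current text.

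**Step 1. Table 12 against Appendix 5.**

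| Event | Table 12 with its footnote | Appendix 5 | Comparison |
|---|---|---|---|
| Colitis, initial Grade 3 | Permanent stop; outside the return route | Withhold, steroids until Grade 1 or lower, taper over at least 1 month, resume; permanent only for Grade 4 or recurrent Grade 3 | Opposite |
| Creatinine, Grade 3 | Discontinue; return possible with sponsor agreement | Withhold, steroids, taper over at least 1 month once at Grade 1 or lower, resume | Table 12 stricter |
| AST, ALT or bilirubin, Grade 3 to 4 | Discontinue; return possible with sponsor agreement | Permanent stop | Appendix 5 stricter |
| Pneumonitis, Grade 3 to 4 | Permanent stop | Permanent stop | Agree |

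Neither source is stricter throughout, so the pattern reveals no implied ranking. Simply placing one above the other would relax at least one row.

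**Step 2. Does the 2-week clause close the colitis gap?** The Appendix 5 route includes a taper of at least 1 month. With the 28-day month used in the maintenance schedule, 28 days exceeds 14 days. Counted from the hold, the requirement for obvious benefit and sponsor agreement therefore applies. It narrows the route but still permits a return that the Table 12 footnote excludes. The same count applies to the Appendix 5 creatinine route, so sponsor agreement is needed on either path there and the practical difference is smaller.

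**Step 3. Restart threshold.** Take a non-hematologic Grade 3 event, outside Table 12's discontinuation list, that improves to Grade 2 within 2 weeks.

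- 5.4.2 read alone: restart is possible at the investigator's discretion, and the sponsor-agreement clause is not reached.
- Tables 6 and 9, and Table 12 where it resumes: still withheld, unless Grade 2 was the baseline.

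The hematologic criteria show no clear conflict.

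**Step 4. Is a precedence stated?** Table 6 defers to Appendix 5 for immune-related events; Tables 9 and 12 carry no such wording. Section 5.4.1 says the worst toxicity governs, but that settles several toxicities at once, not two instructions for one toxicity. The sentence before Table 12 says that the table gives general rules and that action may differ after evaluation by investigator and sponsor; it does not rank the table against Appendix 5.

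**Step 5. Why 5.4.2 is unclear.** Its resumption sentence has been turned into a heading numbered 5.4.3. The reference that follows runs into the section on non-related events, whose text is repeated in full under 5.4.4. The words that evidently completed the reference, pointing to Dose Reductions, are stranded after that block. Rejoined, 5.4.2 sends the reader on to 5.4.5 and its tables.

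**The case against.** The strongest reply is that the Protocol layers its rules. Section 5.4.2 is phrased as a condition that must be met before re-treatment, its intended reference leads to Dose Reductions, and the tables then apply on top. The Grade 2 discretion has a use of its own, because 5.4.2 also covers intolerable Grade 2 events and the start of a new cycle. Table 12 is introduced as general rules open to joint evaluation, late resumption needs the sponsor, and DLT-grade events in Part 2 go to a safety meeting.

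Most of this stands. It makes the Grade 2 point an ambiguity rather than a contradiction, and it means Table 12 should not be described as barring return in every conceivable case. It does not settle colitis: none of these safeguards says which of two opposite instructions applies, and section 3.4 does not require the meeting to take place before a restart.

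Two stronger readings are tempting and are not supported:

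- **That 5.4.2 lets a Grade 4 event resume.** A reader might infer this because the resumption sentence carries no Grade 4 limit. But nothing in 5.4.2 affirmatively allows it. Tables 6 and 9 discontinue at Grade 4, and Table 12 allows only a sponsor-agreed return, with its permanent stops excepted. A minimum followed by a stricter table is not a conflict.
- **That Table 9 re-doses after Grade 3 pneumonitis or liver test elevation in Part 2.** By its title Table 9 covers tremelimumab with AdC68 and pDNA, whereas every Part 2 participant is scheduled to start sasanlimab as well. Table 12 names tremelimumab toxicity with or without sasanlimab, so it still applies if sasanlimab is stopped. Nothing says that Table 9 then takes over.

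**Conclusion.** The concern holds in this form. There is one direct contradiction (initial Grade 3 colitis), two further differences between the same sources (Grade 3 creatinine, and Grade 3 to 4 liver tests), and one ambiguity (the Grade 2 restart discretion in 5.4.2), with no general statement of which rule governs. Sponsor involvement reduces the risk of an unintended re-dose after colitis but does not remove the contradiction. For the Grade 2 restart, the sponsor-agreement clause does not apply within 2 weeks.

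The size cannot be put as a number. Any of the approximately 30 Part 2 participants could meet one of these rules, but the released documents give no event rates for this regimen. The conclusion assumes that Table 12 and Appendix 5 both apply to an immune-related colitis, which the cross-reference in 5.4.5.3 supports.

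**What to change.** 1. **Appendix 5, gastrointestinal section.** Split the combined diarrhea/colitis row. Make Grade 3 colitis a permanent discontinuation, to match Table 12. State the Grade 3 diarrhea rule explicitly: Table 12's permanent-stop footnote does not name diarrhea, and its single-asterisk footnote requires persistence at Grade 3 despite maximal therapy before any modification, so changing the whole row would create a new conflict. The Amendment 1 log, used here only as a sign of intent, records discontinuation for Grade 3 or higher colitis or diarrhea. It supports Table 12 on colitis and shows that the diarrhea rule needs a deliberate decision.
2. **Precedence.** Add one sentence: where 5.4.2, Tables 6, 9 and 12, and Appendix 5 differ, the most restrictive rule applies. For Grade 3 creatinine, return would then need the steroid taper as well as investigator and sponsor agreement. Grade 3 to 4 liver test elevation would be a permanent stop.
3. **Section 5.4.2.** Remove the misplaced heading and the repeated block, restore the reference to Dose Reductions, state that the criteria are minimum conditions, and exclude non-hematologic Grade 3 events from the Grade 2 discretion.

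The cost is protocol wording only. Investigators lose some discretion, and a participant who recovers from an initial Grade 3 colitis could not return to treatment.
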